## **2.2 Pharmacokinetic, Pharmacodynamic and Safety results from MIV-711 First Time in Man Study and Blinded Safety and Tolerability Summary from MIV-711-201**

A First Time in Man (FTIM) study with MIV-711 has been conducted in male and female healthy volunteers including single doses up to 600 mg, multiple doses up to 200 mg once-daily (q.d.) for 7 days and in healthy post-menopausal female volunteers at multiple doses of 100 mg q.d. for 28 days. The single dose part enrolled 18 males and 9 females with an age range of 19-64 years. The multiple dose parts enrolled 15 males and 24 females with an age range of 18-65 years. The primary objective was to determine the safety and tolerability of ascending single and multiple oral doses of MIV-711 in healthy volunteers.

MIV-711 was rapidly absorbed after oral administration with peak concentrations typically occurring 1 hour after administration. A high fat meal prolonged the absorption but had no apparent effect on systemic exposure measured by area under the concentration-time curve from zero to infinity ( $AUC_{\infty}$ ) of MIV-711. The mean terminal half-life was 3.3 to 5.2 hours over the 20 to 200 mg dose range. Observed maximum measured plasma concentration ( $C_{max}$ ) and  $AUC_{\infty}$  increased in close proportion to dose over the single dose range 100-600 mg. Following multiple oral administration of 50 to 200 mg q.d. for 7 days or 100 mg q.d. for 28 days, no accumulation of MIV-711 was observed. MIV-711 was indicated to be extensively metabolised with less than 1% excreted unchanged by the kidney. No gender differences in dose normalised  $C_{max}$  or  $AUC_{\infty}$  for MIV-711 were observed. Further details on MIV-711 metabolism can be found in the IB.

A dose-dependent reduction in the biomarkers serum CTX-I and urinary CTX-II was observed after single and multiple doses of MIV-711, by down to 55 and 72% from Baseline respectively at multiple dosing (for further details see Section 2.4, Section 2.5 and the IB).

No clinically meaningful effects on vital signs, laboratory parameters or electrocardiogram (ECG) time intervals: including QTc interval (Fridericia's correction; QTcF) were observed. Adverse events (AEs) assessed as related to investigational medicinal product (IMP) had a similar incidence for active treatment and for placebo. One subject was found on a per protocol ECG to have asymptomatic atrial fibrillation after 3 q.d. doses of MIV-711 200 mg. Spontaneous conversion to sinus rhythm occurred within 24 hours after the last dose. Investigations by an independent cardiologist supported that the post-dose atrial fibrillation observed was possibly drug induced. Further details of the results of the FTIM study are provided in the IB.

The ongoing MIV-711-201 study, from which the patients in the current protocol will be recruited, will include 240 patients under 1:1:1 randomisation to placebo: 100 mg MIV-711: 200 mg MIV-711. The first patient was randomised in March 2016 and recruitment is ongoing; as of 21 June 2016, 102 patients have been enrolled. No treatment-related serious adverse events (SAEs) have been reported to date. One unrelated SAE was reported before the start of dosing. Seven patients were withdrawn from the study due to the following reasons: increased liver function tests; severe polymyalgia; suspected macular-papular rash; angioedema; non-compliance; lost to follow-up; withdrawal of consent. No safety-related trends have been identified in the ongoing Study MIV-711-201 and it is believed that MIV-711 has acceptable safety and tolerability based on blinded results in OA patients.

### 2.3 Study Rationale

As stated in Section 2.1, there are no pharmacological treatments available today that provide long term relief of OA symptoms nor are there any treatments that counteract its structural progression. Disease modifying OA drugs (DMOADs) would potentially address both these features which highlights the importance of evaluating candidate drugs such as MIV-711.

The available data support the hypothesis that a potent and selective inhibitor of cathepsin K such as MIV-711 will have both anti-resorptive effects on subchondral bone and protective effects on cartilage; this is supported by relevant animal models which demonstrate reduced structural joint degradation after treatment with MIV-711.

Whilst the first study of MIV-711 in patients, Study MIV-711-201, has the potential to establish a first indication of disease modifying efficacy for MIV-711 in OA, it is also important to consider the chronic nature of OA which often leads to life-long disease symptoms from the time of diagnosis. The life-long course of OA highlights the need to assess long-term safety for a prospective DMOAD, which is therefore the main rationale of the current extension study. While further outlining the current study MIV-711-202 in the following sections, the study population pertaining to the 12 month safety assessment in Study MIV-711-202 is henceforth described as Study Population A.

There are two further rationales for this study:

- It is known that cartilage structural changes are not expected to be apparent over a 6-month period using MRI [35] which constitutes the reason for using knee joint bone area as the main structural read-out in Study MIV-711-201. In the current study, patients will be treated for 52 (26+26) weeks (Study Population A) which will enable the secondary analysis of cartilage changes versus Baseline in Study MIV-711-201.
- Furthermore, there is no available method to predict OA progression. In Study MIV-711-201 there is a potential to identify patients treated with placebo that exhibit signs of clinical progression over the course of 26 weeks. Patients with manifest symptomatic progression of OA would constitute the most justifiable patient population to receive a DMOAD. It is believed that the proposed extension study would be the first opportunity to explore the effects of a potential DMOAD in OA

patients with verified progressive symptoms (based on symptoms reported from Study MIV-211-201). While further outlining study MIV-711-202 in the following sections, the study population pertaining to the 6 month treatment assessment in patients with progressive symptoms is henceforth described as Study Population B.

## 2.4 Study Design and Dosing Rationales

The present study is a 6-month open-label one-arm extension study evaluating safety and tolerability as well as the efficacy of 200 mg MIV-711 q.d. in two separate patient populations denoted as Study Populations A and B.

Study Population A will be recruited from patients treated with 200 mg MIV-711 q.d. in Study MIV-711-201 and whose symptoms did not clinically significantly deteriorate as defined by an increase in the numeric rating scale (NRS) of  $\leq 2$  compared to Baseline. Patients eligible for Study Population A will be offered to roll over for 6 months' extended treatment, primarily evaluating longer term safety and tolerability. The total treatment duration of 52 weeks also allows a more suitable treatment length for the exploratory study of any structural effects of MIV-711 on joint cartilage thickness. [23, 24, 25].

There will be no continuation of the 100 mg dose from Study MIV-711-201 because from a safety and tolerability perspective, using the 200 mg dose in this extension study allows exposure to the highest dose previously tested for MIV-711. MIV-711 has also shown a higher reduction in CTX-II excretion at 200 mg compared with 100 mg q.d. Based on the established link between CTX-II and the levels that are predictive for structural effects on bone only, and the higher levels that are indicative of cartilage protection (see Section 2.1), it is judged that the 200 mg dose should be studied in this extension study since it has the highest potential to contribute to a disease modifying effect in OA. Extending the 200 mg dose in those patients that did not significantly deteriorate clinically in their OA on that dose during the first 26 weeks, allows a balanced assessment of the 52-week safety and tolerability of MIV-711 while at the same time maximizing the opportunity of measuring structural change on joint cartilage thickness versus Baseline. Joint cartilage thickness is believed to require an observational period of at least 12 months as described in the literature.[23, 24, 25]

A further rationale of this study is to explore the treatment effect in a group of OA patients that have confirmed symptom progression over the last 6 months (Study Population B). Study Population B will be recruited from patients receiving placebo in Study MIV-711-201 having experienced a clinical worsening as defined by an increase in NRS of  $\geq 2$  versus Baseline. Patients eligible for Study Population B will be offered 200 mg MIV-711 q.d. for the next 26 weeks. In addition to offering the treatment to appropriate patients, this also enables the assessment of the effects of MIV-711 based on MRI imaging, symptoms and biomarkers in patients with progressing symptoms and, as such, has the potential to provide valuable information for future patient selection in OA trials. Similar to Study MIV-711-201, the joint structural endpoint of choice over 6 months treatment constitutes MRI joint bone surface measurement (see Section 7.2).[23] All analyses, with the exception of safety and tolerability, will be conducted as exploratory with regards to Study Population B.

All patients in Study MIV-711-201 at the participating sites included in Study MIV-711-202 will be given the opportunity to participate. Patients, investigators and site staff will not be made aware of the preceding treatment allocation in Study MIV-711-201 and treatment will remain blinded until database lock of study MIV-711-201. The actual roll-over of individual patients to Study MIV-711-202 is based on the criteria for Study Populations A and B detailed above and is executed by a central person independent from the study with access to the randomisation list and eCRF for Study MIV-711-201. The patients will be considered for roll-over one by one as they complete the last treatment visit in Study MIV-711-201 and upon blinded approval of the investigator as well as provision of informed consent. Based on the

selection criteria for Study Population A and B described earlier in this section, it is anticipated that 50-80 patients will be eligible for participation. Patients will be recruited from up to 5 centres in up to 5 countries for this study. Recruitment may be terminated if considered appropriate or necessary by the sponsor.

The analysis of data from the proposed study will not be based on a formal statistical analysis since the primary endpoint constitutes safety and tolerability. All efficacy parameters measured in Study MIV-711-201 will also be measured in the proposed study. However, the important difference is that any comparisons will be made from baselines within but not between Study Population A and B. In contrast, in Study MIV-711-201, comparisons will be made between treatment groups with a formally powered analysis regarding the primary endpoint.

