A central person, independent from the study, with access to the randomisation list and the eCRF for the MIV-711-201 study will confirm Inclusion Criterion 1. The confirmation will be communicated to the site staff and the study team via fax/email without revealing the treatment in MIV-711-201 or the change in NRS score.

All enrolled patients will receive 200 mg q.d. oral dose of MIV-711 for 26 weeks in addition to their current medication. MIV-711 200 mg will be provided as identical capsules to those used in Study MIV-711-201.

The patients will take the last dose of IMP in Study MIV-711-201 at Visit 8 and dosing in the present study will be started at Visit 2 after a screening period of  $10 \pm 5$  days.

Patients who are not eligible to participate in the present study will return for the safety follow up visit (Visit 9) in Study MIV-711-201.

Patients will be permitted to remain on their current analgesic regimen with any changes in concomitant medications reported and recorded at study visits as well as in a patient-reported daily e-diary for two 2-week periods prior to Visit 4 and Visit 5.

The study consists of a Screening period of approximately 2 weeks (Visit 1), eligibility at Visit 2, an open-label treatment period of 26 weeks from Visit 2 through Visit 5, and a follow-up period of 4 weeks (Visit 6) after the last dose of study treatment is administered. Telephone calls will be made 5-9 days after all dosing visits for safety and tolerability. There will be additional phone calls at Week 10 and Week 20 for safety and tolerability.

A Data Monitoring and Ethics Committee will meet to review the unblinded safety and tolerability data after the first 25 patients complete Visit 4 and Visit 5.

Treatment	All patients will receive a 200 mg oral dose of MIV-711 q.d. for 26 weeks in addition to their current medication.
Number of Patients	All patients in Study MIV-711-201 at the participating sites included in Study MIV-711-202 will be given the opportunity to participate provided that they meet the eligibility criteria. However, based on the inclusion and exclusion criteria it is anticipated that 50-80 patients will be eligible for participation. The patients will be recruited from up to 5 centres in up to 5 countries for this study.

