### 5.1 Inclusion Criteria

Patients must meet all of the following criteria to be eligible for enrolment in this study:

1. Previously enrolled in Study MIV-711-201 including completion of Visit 8 either by
  - Receiving MIV-711 200 mg and had non-significant clinical worsening on the primary endpoint as defined by NRS increase of  $\leq 2$

OR by

- Receiving placebo and had a clinically significant worsening on the primary endpoint as defined by NRS increase of  $\geq 2$

The NRS result will be derived using the primary endpoint from Study MIV-711-201: NRS average knee pain in the target knee with 7 days recall: increase from Baseline (Visit 2 of Study MIV-711-201) to Visit 8 of Study MIV-711-201.

2. Female patients must be non-pregnant, non-lactating and of non-childbearing potential either as naturally (spontaneously) post-menopausal or due to hysterectomy and/or bilateral oophorectomy/salpingo-oophorectomy (as determined by patient medical history). Naturally (spontaneously) post-menopausal is defined as being amenorrhoeic for 12 months without an alternative medical cause and with a Screening follicle stimulating hormone test indicating post-menopausal state.
3. Male patients should avoid fathering a child by either of the following methods:
  - True sexual abstinence: meaning that heterosexual abstinence is in line with the preferred and usual lifestyle of the patient (periodic abstinence such as that based on calendar, ovulation, symptothermal, post-ovulation methods, declaration of abstinence for the duration of a trial, or withdrawal/coitus interruptus are not acceptable methods of contraception).
  - Willingness to use two effective means of contraception with their partner from the time of first IMP administration until 3 months after the last dose of IMP. Two or more of the following methods are acceptable and must include at least one barrier method: i) Surgical sterilisation (i.e., bilateral tubal ligation for female partners; vasectomy for male), ii) placement of an intrauterine device or intrauterine system, iii) hormonal contraception (implantable, patch, oral), iv) barrier methods including condom or occlusive cap (diaphragm or cervical/vault caps) with spermicidal foam/gel/film/cream/suppository. Male patients who have been sterilised are required to use one barrier method of contraception (condom).

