### Pain, function and disease activity

- 11-point NRS scales for:
  - Average overall knee pain severity in the target knee over the past 1 week
  - Average overall knee pain severity in the contralateral knee over the past 1 week
  - Worst knee pain severity in the target knee over the past 1 week
  - Global disease activity over the past 1 week
- ICOAP – an 11-item tool designed to assess constant and intermittent pain
- WOMAC 3.1 – a 24-item OA - specific, tri-dimensional self-administered questionnaire, for assessing health status and health outcomes in OA of the knee
- In an e-diary format, a patient pain diary and analgesia questionnaire will be completed daily during two 2-week periods prior to Visit 4 and prior to Visit 5.

Using a 6-point Likert scale (completely better, much better, better, no change, worse, much worse) we will record patient-reported:

- Global improvement in knee problem at follow-up
- Global improvement in knee pain at follow-up
- Global improvement in knee function at follow-up

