4.1 Study Schedule MIV-711-201

Study Visit	V1	V2	V3	V4	V5	V6	V7	V8	V9
Weeks	-4	1	2	4	8	14	20	26	30
Day	up to 30 days	Day 1	day 15 ±2 days	day 29 ±2 days	day 57 ±2 days	±7 days	±7 days	±7 days	± 7 days
Visit Description	Screening	Randomisation/ Baseline	Treatment period						Safety follow- up
Signed informed consent	X								
Randomisation		X							
Inclusion/exclusion criteria	X	X							
Target knee identification ^A	X								
Demographics	X								
Weight	X							X	
Height	X								
Medical & Surgical history	X								
Physical examination	X	X	X ^B	X ^B	X	X	X ^B	X	
Vital signs, including body temperature	X	X	X	X	X	X	X	X	X
12-Lead ECG ^C	X	X	X	X	X	X	X	X	X

PAREXEL International Statistical Analysis Plan

Medivir
Protocol: MIV-711-202

Final 1.0
16 January 2018

Study Visit	V1	V2	V3	V4	V5	V6	V7	V8	V9
Weeks	-4	1	2	4	8	14	20	26	30
Day	up to 30 days	Day 1	day 15 ±2 days	day 29 ±2 days	day 57 ±2 days	±7 days	±7 days	±7 days	± 7 days
Visit Description	Screening	Randomisation/ Baseline	Treatment period						Safety follow- up
Clinical chemistry/ Haematology	X	X	X	X	X	X	X	X	X
Urinalysis ^D	X	X	X	X	X	X	X	X	X
Urine drug screen	X				X				
Post-menopausal assessment (females only)	X								
HBsAg, anti-HBc, anti-HBs, HCV, and HIV test	X								
e-diary dispensing and training	X								
Patient Emergency Card dispense	X								
MRI of target knee ^E		X						X	
e-diary for pain and analgesic ^F		X				X		X	
Duration and onset of knee pain		X							
NRS, ICOAP, WOMAC	X ^G	X			X	X		X	X ^G

PAREXEL International Statistical Analysis Plan

Medivir
Protocol: MIV-711-202

Final 1.0
16 January 2018

Study Visit	V1	V2	V3	V4	V5	V6	V7	V8	V9
Weeks	-4	1	2	4	8	14	20	26	30
Day	up to 30 days	Day 1	day 15 ±2 days	day 29 ±2 days	day 57 ±2 days	±7 days	±7 days	±7 days	± 7 days
Visit Description	Screening	Randomisation/ Baseline	Treatment period						Safety follow- up
Global improvement (6-point Likert scale)					X	X		X	
EuroQoL EQ-5D-5L		X						X	
Brief Medication Questionnaire					X	X		X	
Dispense IMP ^J		X ^H			X	X			
Drug accountability		X			X	X		X	
PK sampling (blood)				X				X	
Biomarker samples ^J		X		X		X		X	X
AEs/SAEs monitoring	X	X	X	X	X	X	X	X	X
Concomitant Medication		X	X	X	X	X	X	X	X
Phone call to assess safety and tolerability ^K		X	X	X	X	X	X		
Blood sample for pharmacogenomics, proteomics, genomics, metabolomics and lipidomics and urine sample for proteomics and metabolomics ^L		X						X	

PAREXEL International Statistical Analysis Plan

Medivir
Protocol: MIV-711-202

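### Eligibility for the extension, combined with a patient's own NRS change, usually allows the Study 201 arm to be inferred before 201 database lock, contrary to Protocol Section 2.4

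*Protocol*

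**What the plan says.** Protocol Section 2.4 states that "Patients, investigators and site staff will not be made aware of the preceding treatment allocation in Study MIV-711-201" and that "treatment will remain blinded until database lock of study MIV-711-201". The same section has patients considered for roll-over one at a time, as each completes the last 201 treatment visit. An independent central person who holds the randomisation list and the 201 eCRF does the check.

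The Synopsis and Section 4 describe the safeguard. Confirmation of Inclusion Criterion 1 goes to the site staff and study team "without revealing the treatment in MIV-711-201 or the change in NRS score".

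Section 5.1 gives two routes through Criterion 1:

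- "Receiving MIV-711 200 mg and had non-significant clinical worsening on the primary endpoint as defined by NRS increase of" 2 or less (Study Population A, Group A in the SAP);
- "Receiving placebo and had a clinically significant worsening on the primary endpoint as defined by NRS increase of" 2 or more (Study Population B, Group B in the SAP).

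The variable is "NRS average knee pain in the target knee with 7 days recall: increase from Baseline (Visit 2 of Study MIV-711-201") to Visit 8. Section 2.4 also says that the 100 mg dose is not continued, so that arm has no route in.

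**The concern.** Each route ties one arm to one direction of change, and both are printed in the protocol that the sites use. The notice leaves out the arm and the NRS change, but the change is the patient's own answer, given at two 201 clinic visits. If the site or the patient has those two answers, the missing item can be restored and the arm follows.

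At stake is the blind of Study 201, the randomised study with the formally powered analysis (Section 2.4). Notices go out while that study is running. An investigator could then complete, revise or answer queries on a patient's 201 adverse-event severity and causality with the arm in mind. A patient refused under Criterion 1 returns for 201 Visit 9, where adverse events and knee-pain NRS are still collected (SAP Section 4.1).

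**Working it through.** **Inputs from the documents**

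- Criterion 1 routes: Protocol Section 5.1.
- Scale: Protocol Section 7.9 specifies "11-point NRS scales for" average knee pain, scored 0 to 10, so changes are whole numbers.
- Collection: the row "NRS, ICOAP, WOMAC" in the 201 schedule (SAP Section 4.1) is marked at Visits 2 and 8.
- 201 size: 240 patients randomised 1:1:1 (Protocol Section 2.2), so 240/3 = 80 per arm.
- Timing: first 201 randomisation in March 2016, with 102 of 240 enrolled at 21 June 2016 (Section 2.2); Study 202 runs from September 2016 (Section 10.11).

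**Step 1: which arms remain possible**

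| NRS change | Criterion 1 confirmed | Criterion 1 not confirmed |
|---|---|---|
| +1 or less, or a fall | 200 mg only | placebo or 100 mg |
| exactly +2 | 200 mg or placebo | 100 mg only |
| +3 or more | placebo only | 100 mg or 200 mg |

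This needs no statistical model. Among confirmed patients, only +2 is ambiguous. A refusal identifies the arm only at +2; otherwise it excludes one arm.

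**Step 2: timing**

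Twenty-six weeks from March 2016 is September 2016, when 202 opens. At 21 June 2016, 240 - 102 = 138 patients were still to be enrolled. Anyone starting after that date reaches Visit 8 around 20 December 2016 or later. Notices therefore begin months before 201 can lock, while other patients are on blinded treatment.

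**Step 3: how many patients**

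The only nearby plan figure is 50 to 80 eligible patients. It cannot be reproduced, because no worsening rate, uptake or number of 201 patients at the participating sites is given. Against 160 patients in the two relevant arms it implies 50/160 = 31% to 80/160 = 50%.

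The documents also give no distribution of NRS change, so one is assumed: a normal variable rounded to whole numbers, with the same mean m and SD s in both arms. Then

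- P(change = 2) = Φ((2.5 - m)/s) - Φ((1.5 - m)/s)
- P(change ≤ 2) = Φ((2.5 - m)/s)
- P(change ≥ 2) = 1 - Φ((1.5 - m)/s)
- share deducible = 1 - [P200(=2) + Pplacebo(=2)] / [P200(≤2) + Pplacebo(≥2)]

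The 80 per arm cancels from the share.

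Worked case, m = -1 and s = 2: P(=2) = Φ(1.75) - Φ(1.25) = 0.960 - 0.894 = 0.066, or 5.25 of 80 in each arm. Group A eligible = 80 × 0.960 = 76.8. Group B eligible = 80 × 0.106 = 8.45.

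- Overall: 1 - 10.5/85.25 = 88%
- Group A: 1 - 5.25/76.8 = 93%
- Group B: 1 - 5.25/8.45 = 38%

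Over the assumed ranges:

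| Mean | SD | Eligible A / B | Overall | Group A | Group B |
|---|---|---|---|---|---|
| 0 | 1.5 | 76.2 / 12.7 | 80% | 88% | 30% |
| 0 | 2 | 71.5 / 18.1 | 78% | 86% | 47% |
| 0 | 2.5 | 67.3 / 21.9 | 79% | 86% | 58% |
| -1 | 1.5 | 79.2 / 3.8 | 93% | 96% | 21% |
| -1 | 2 | 76.8 / 8.5 | 88% | 93% | 38% |
| -1 | 2.5 | 73.5 / 12.7 | 86% | 92% | 51% |
| -2 | 1.5 | 79.9 / 0.8 | 98% | 99% | 14% |
| -2 | 2 | 79.0 / 3.2 | 95% | 97% | 31% |
| -2 | 2.5 | 77.1 / 6.5 | 91% | 95% | 45% |

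A wider grid (placebo mean -2 to +1, 200 mg mean -3 to +1, SD 1.5 to 3) gives 65% to 99% overall, 75% to nearly 100% in Group A and 14% to 71% in Group B. For the arm to be hidden in at least half of those enrolled, 25 of 50 or 40 of 80 would have to sit at exactly +2. No case on either grid comes near that.

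**The case against.** The strongest reply is that the documents never say the site can see the 201 scores. The 201 protocol is not available, and withholding the change from the notice could mean that the sponsor believes sites lack it. A patient would also have to recall a score given 26 weeks earlier. This stands as a limit: access is inferred from a clinic-visit questionnaire for which no masking is described.

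The proportions rest on an assumed distribution. The nine cases give 81 to 90 eligible patients, above the protocol's 50 to 80, because they ignore uptake and the restriction to participating sites. That also stands. The enumeration in Step 1 does not depend on it, although the overall share depends on the mix of Groups A and B.

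Several stronger readings are tempting, and the documents do not support them.

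- **The notice reveals the arm.** It does not; the Synopsis and Section 4 describe it accurately. The arm follows only when the NRS change is added.
- **Withholding the change hides nothing.** Anyone without the scores learns no individual arm, and many Group B patients stay ambiguous at +2.
- **The 201 primary endpoint is compromised.** The central person checks Criterion 1 against the 201 eCRF, so the Visit 8 score is recorded before a notice can go out. MOAKS is read centrally, rolled-over patients skip 201 Visit 9, and adverse events from 202 consent onward go into the 202 eCRF (Section 7.13.2.5).
- **The 202 results are undermined.** Study 202 is open-label, all patients knowingly take 200 mg, and the protocol plans descriptive summaries with no comparison of A with B. The promise ends at 201 lock in any case.
- **Other 201 patients are unblinded.** One patient's arm does not identify another's.

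**Conclusion.** The Section 2.4 statement is stronger than the design can deliver. If the site or patient knows the Visit 2 to Visit 8 NRS change, a Criterion 1 confirmation fixes the 201 arm unless the change is exactly +2, and a refusal at exactly +2 implies 100 mg. Under the stated assumptions this covers about 78% to 98% of eligible patients (65% to 99% on the wider grid). Group A accounts for most of it. The word most cannot be assumed for Group B alone, where the share is 14% to 58% on the main grid.

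The consequence is moderate. The exposure lies mainly in 201 adverse-event severity and causality entries and query answers made after the notice, and in Visit 9 data of refused patients. The documents do not allow its size to be estimated. No primary result of either study is invalidated, but the remedy is cheap and a stated blinding property should be true.

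**What to change.** 1. Do not send the Criterion 1 confirmation until the site has entered, and the investigator has signed, that patient's 201 Visit 8 patient-reported outcomes and all adverse-event severity and causality assessments to date. Audit-trail any later change and flag it as made after the notice.
2. Replace the Section 2.4 statement. Say that the notice does not state the arm, but that eligibility combined with the NRS change can allow it to be inferred before 201 lock.
3. Report this as a limitation for 201 adverse-event causality.

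The cost is a wording change and some added data management inside the 10±5 day screening period. That period can be as short as 5 days, so a full query-and-freeze of the 201 record may not fit; entry and signature is the lighter requirement. Events still ongoing cannot be final at that point, hence the flag on later changes. The arm remains inferable afterwards: the change protects data recorded before the notice and does not restore the blind.
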